3.3.3 Case-control comparison

An analysis of the qualitative GenScript result with the 145 patients that will be used for the nested case-control study found a significant difference ($p=0.002$) in the time to sustained recovery, with a sub-hazard ratio of 1.91 (95% CI: 1.35, 2.7) for baseline serostatus, indicating that seropositive patients had a quicker time to sustained recovery. (This used the Fine-Gray approach to modelling competing risks). The quantitative result from this assay also demonstrated a statistically significant association with time to sustained recovery and adjustment for study level effects did not impact the associations meaningfully. An analysis of case control status also detected an odds ratio that was significantly different from 1 ($p=0.015$) with an odds ratio of 2.34 (95% CI: 1.18, 4.65).

With a sub-hazard ratio of 1.91, 104 events provide 90% power for rejecting the null hypothesis that the sub-hazard ratio is 1, and this number of events provides 80% power for a sub-hazard ratio of 1.75. An analysis of case control status has lower power and would require an odds ratio of 2.72 to have 80% power for detecting an association between baseline antibody levels and case control status with this sample size (larger than what was observed for the GenScript assay).

3.4 Participant Selection for the Field Test

Interested sites will be selected based on their ability to recruit patients that meet the eligibility criteria for TICO. Planned enrollment into TICO is not necessary for participation in the field test. All participants will need to consent to participate in the field test component of the protocol, including those co-enrolled in TICO. The inclusion and exclusion criteria for the field test are as follows:

3.4.1 Inclusion criteria

1. Age ≥ 18 years.
2. Informed consent by the patient or the patient's legally authorized representative (LAR) for up to 4 fingersticks for POC testing and a blood draw for stored blood samples.
3. SARS-CoV-2 infection, documented by a nucleic acid test (NAT) or equivalent testing within 3 days prior to consent OR documented by NAT or equivalent testing more than 3 days prior to consent AND progressive disease suggestive of ongoing SARS-CoV-2 infection per the responsible investigator. (For non-NAT tests, only

those deemed with equivalent specificity to NAT by the protocol team will be allowed. A central list of allowed non-NAT tests is maintained for TICO and that list will also be used for this protocol.)

4. Duration of symptoms attributable to COVID-19 ≤ 12 days per the responsible investigator.
5. Requiring admission for inpatient hospital acute medical care for clinical manifestations of COVID-19, per the responsible investigator, and NOT for purely public health or quarantine purposes.

3.4.2 Exclusion criteria

1. Prior receipt of SARS-CoV-2 hIVIG, convalescent plasma from a person who recovered from COVID-19, or SARS-CoV-2 nMAb within 6 months of the blood draws for testing as part of this protocol.
2. Disease severity beyond that of stratum 1 in the TICO trial.

This includes the following conditions:

- a. stroke
- b. meningitis
- c. encephalitis
- d. myelitis
- e. myocardial infarction
- f. myocarditis
- g. pericarditis
- h. symptomatic congestive heart failure (CHF; New York Heart Association [NYHA] class III-IV)
- i. arterial or deep venous thrombosis or pulmonary embolism

Or current requirement for any of the following:

- a. high-flow supplemental oxygen
- b. non-invasive ventilation
- c. invasive mechanical ventilation
- d. extracorporeal membrane oxygenation
- e. mechanical circulatory support
- f. vasopressor therapy
- g. commencement of renal replacement therapy at this admission (i.e., not patients on chronic renal replacement therapy).

3. In the opinion of the responsible investigator, any condition for which, participation would not be in the best interest of the participant or that could limit protocol specified assessments.

A blood specimen for storage is required for participation in the study.

These eligibility requirements are nearly identical to those used in the TICO trial from which specimens will be used for the case-control study. One major difference is that TICO participants must agree to not participate in other COVID-19 treatment trials until after Day 5 (this is clearly not relevant for this protocol). The exclusion criteria here are more restrictive than those in the TICO trial. This is so participants in this protocol are comparable to those who enrolled in the TICO trials from whom specimens will be used for the case-control study. Those trials had more restrictive exclusion criteria than listed in the TICO protocol at the request of the FDA and match the exclusion criteria listed here. This will facilitate interpretation of analyses that use specimens from the field test and from the previously conducted trials. Eligibility criteria were also selected to be similar to those in the TICO trial to ensure these results are relevant for

future trials in hospitalized patients conducted by INSIGHT and aligned networks for which eligibility criteria are likely to be similar to TICO.

Participant characteristics will be monitored during data collection and adjustments to the characteristics of those recruited for participation may be made.

3.5 Data and Blood Collection Plan

After providing written informed consent, a CRF will be completed for each participant and blood will be collected by up to 4 fingersticks and by a venous blood draw of 9 mL (in an EDTA collection tube for aliquoting plasma after centrifugation into 4 2 mL cryovials, each with about 1 mL of plasma). The blood from the fingersticks will be used to conduct the POC tests and the plasma cryovials will be stored locally in a -70°/-80° freezer until they can be shipped to the central biorepository. The CRF will capture the outcome of the POC tests, the length of time from the start of the assay to recording the test outcome, and selected data collected on the TICO Screening and Baseline and Randomization forms. This will include

1. Participation in other INSIGHT studies.
2. Demographics.
3. Date of onset of COVID-19 symptoms.
4. Severity of COVID-19.
5. Oxygen requirements.
6. History of chronic comorbidities.
7. SARS-CoV-2 vaccination information.
8. Targeted concomitant medications.
9. Height and weight.

Two fingerstick samples of blood will be obtained, one for each POC test. The plasma samples collected will be used for determination of antibody and antigen levels, and central laboratory determination of the two POC tests.

All study procedures will be performed by study personnel. Training materials and the consent document will clearly state that the results of the POC tests are not to be used for patient management and so should not be shared with the patient or care giver. All study procedures must be performed within 24 hours of completing the written informed consent.

Information will be collected from site staff about ease of use of each platform.

4 Data Analysis

4.1 Field Evaluation of Platforms: Ease of Use, Time for Test Result

The number and proportion of failed tests and tests not obtained within 20 minutes will be determined overall and for each site. The median and interquartile range of the time from the start of the assay to recording of the test outcome on the CRF will be determined overall and for each site.

4.2 Local versus Central POC Test Result Comparison

The primary analysis will test if the odds ratio for the association is 1 using McNemar's chi-square test with a significance level of 0.05. Samples for which either test result is missing will be excluded from this analysis. This test will be supplemented by a 95% CI for the difference in the probability of testing positive. Site level effects will be estimated by using generalized estimating equations for Bernoulli outcomes using a logistic link with pairs of results modelled as

being correlated (the test outcome is the binary outcome). This model will include fixed effects for the test type (i.e., local or central) and site. Sites may be grouped based on geography or ICC membership to improve the precision of site level estimates and the interaction between site and test type will be investigated. Subgroups based on age, existence of an immunocompromising condition and vaccination status will be investigated (provided enough individuals with an immunocompromising condition enroll). These subgroup analyses will test for an interaction between group membership and test type. This analysis will be used for both POC tests, and there will not be an adjustment for the conduct of the 2 sets of analyses.

In addition to the primary analysis, associations between test results and participant characteristics will be investigated. These characteristics include age, sex, existence of an immunocompromising condition and vaccination status.

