The primary objective of the field test is to test for an association between the outcome of the locally obtained POC test and the centrally obtained result from the GenScript assay on a blood sample obtained at the same time as the sample for the POC tests.

The primary objective of the nested case-control study is to test for an association between the POC test result on stored baseline specimens and the primary efficacy outcome in TICO on a subset of specimens from TICO participants for whom the GenScript assay result has already been determined. Since conducting POC assays on large numbers of stored specimens is time consuming (since each assay takes 10-20 minutes and

each individual specimen must be analysed), a case-control design will be utilized. The case definition is death or time to sustained recovery that exceeds 28 days. To maximize the difference between cases and controls, controls are defined as those with a time to sustained recovery of no more than 16 days. With these definitions there are 68 cases and 77 controls for a total sample size of 145. Of these participants, 104 experienced a sustained recovery (the primary outcome in TICO) and 20 died.

DURATION

Participants in the cross-sectional study will be completed with the study within 24 hours of consent. Actual participation will just involve the consent process, 2 POC tests, and completion of a case report form (CRF) and a blood draw, thus we expect participation to last no more than a few hours.

SAMPLE SIZE

Sample size for the cross-sectional study is targeted at 375. With this sample size the study will have 83% power for detecting a difference in the probability of a positive test between 2 assays when the odds ratio for the 2 assays is 2.6 and the smaller of the 2 probabilities of test discordance is 3%.

The sample size for the nested case-control study is 145. Analysis of the case-control population using the GenScript assay detected a sub-hazard ratio of 1.91. With a sub-hazard ratio of 1.91, 104 events provide 90% power for rejecting the null hypothesis that the sub-hazard ratio is 1 and this number of events provides 80% power for a sub-hazard ratio of 1.75.

POPULATION

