3.2 Study Objectives

3.2.1 Field test

The overall objective of the field test is to determine if a POC test can be used to identify individuals who lack endogenous antibodies. The **primary objective** is to test for an association between the outcome of the locally obtained POC test and the centrally obtained result from the GenScript assay on a blood sample obtained at the same time as the sample for the POC test. There are also a number of secondary objectives that will investigate the feasibility of this approach, and others that will help interpret the outcome of the primary objective. These are as follows:

1. Determine the frequency with which the POC test fails to give an unambiguous result.
2. Determine the time required to obtain a POC result.
3. Determine the magnitude of the association between the locally obtained POC test result by the 20-30 sites and the same POC assay on the same specimens determined centrally after processing, freezing, storing, and shipping.
4. Determine the magnitude of the association between the POC test result and the GenScript assay on the same specimens both determined centrally.

Secondary objective 3 will provide information on the impact of processing (centrifugation for plasma), freezing, storing, and shipping on the test results using the same assay while secondary objective 4 will provide a head-to-head comparison of the assays using the same specimen subjected to the same handling procedures. Specimen handling and the specific assay used both likely contribute to differences we may observe between the local POC test and the results from the GenScript assay.

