3.3.2 Local and central POC test result versus GenScript cPass assay result

Sample size considerations for these comparisons are similar to those from the previous section, but we do have data from 302 participants on the relationship between the central POC test using the RightSign platform and the GenScript assay using stored specimens for both assays. The association depends on which isotype is measured with the RightSign assay: there is evidence that the odds ratio is different from 1 for IgM (odds ratio 7.5, $p<0.001$) but not for IgG (odds ratio 1.1, $p=0.82$). These preliminary data indicate that 375 samples obtained as part of the field test will provide more than adequate power for detecting a difference for the GenScript assay and RightSign IgM assay and very low power for detecting a difference between the GenScript assay and the RightSign IgG assay due to the high degree of association between the latter pair of assays.

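### The field test's primary label, 0.05 level and 83% power scenario sit under local versus central POC (secondary objective 3), not under the stated primary objective, local POC versus GenScript

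*Combined protocol and SAP*

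**What the plan says.** **Objective.** Section 3.2.1 gives the field test's primary objective as "to test for an association between the outcome of the locally obtained POC test and the centrally obtained result from the GenScript assay", and Section 1 agrees. Third among the secondary objectives is: "Determine the magnitude of the association between the locally obtained POC test result by the 20-30 sites and the same POC assay", run centrally after handling and shipping.

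**Analysis.** Section 4.2 is headed as the local versus central POC comparison. It states: "The primary analysis will test if the odds ratio for the association is 1", by "McNemar's chi-square test with a significance level of 0.05". It excludes pairs with a missing result, defines test type as local or central, and declines any adjustment for analysing two platforms. Section 4.3 compares local and central POC results with GenScript by McNemar's test with 95% confidence intervals, and refers back to Section 4.2 for site and subgroup work. It calls nothing primary and gives no significance level or missing-pair rule.

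**Power.** Section 3.3.1, headed local versus central POC, develops Table 5 and the scenario with odds ratio 2.6 and p01 = 0.03. It notes that no data exist for this comparison. The sample size paragraph of Section 1 says "the study will have 83% power for detecting a difference in the probability of a positive test between 2 assays" in that scenario, without saying which two. Section 3.3.2 covers POC versus GenScript. It calls the considerations similar to those of 3.3.1 and cites 302 participants with central RightSign and GenScript results on stored specimens (odds ratio 7.5 for IgM, 1.1 for IgG). It rates power as more than adequate for IgM and as "very low power for detecting a difference between the GenScript assay and the RightSign IgG assay" for IgG.

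**The concern.** The plan's objective and its designated primary analysis answer different questions. One asks whether a bedside POC result tracks the GenScript result. The other asks whether centrifugation, freezing and shipping change the result of the same POC assay. Section 3.2.1 treats the second as an aid to interpreting the first.

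Followed literally, the field test would report a specimen-handling comparison as its primary result. The 83% in Section 1, which comes after the statement of the GenScript objective, would naturally be read as the power for that objective. If the mismatch is settled only after data are seen, the choice of primary comparison is open to selective reporting.

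**Working it through.** **1. The passages side by side**

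| Element | Local POC v GenScript | Local v central POC |
|---|---|---|
| Rank in 3.2.1 | Primary objective | Secondary objective 3 |
| Called primary in Section 4 | No (4.3) | Yes (4.2) |
| Significance level stated | No | 0.05 |
| Missing-pair rule | No | Yes |
| Power section | 3.3.2, in words | 3.3.1, numeric |
| Preliminary data | 302 participants, central RightSign only | None |

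**2. Reproducing the 83%**

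Inputs from 3.3.1: N = 375, p01 = 0.03, odds ratio 2.6. A two-sided 0.05 level is assumed, because sidedness is not stated. Schlesselman's formula, without continuity correction:

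- m = N × p01 × (1 + OR) = 375 × 0.03 × 3.6 = 40.5 expected discordant pairs
- P = OR/(1 + OR) = 2.6/3.6 = 0.722
- power = Φ{(|P − 0.5|√m − 1.96/2)/√[P(1 − P)]} = Φ{(0.222 × 6.364 − 0.98)/0.448} = Φ(0.969) = 0.834

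This matches the stated 0.83, and all 21 cells of Table 5 reproduce to rounding. The formula does not depend on which pair of results is compared. At odds ratio 2.6 it gives 0.36, 0.83 and 0.97 for p01 = 0.01, 0.03 and 0.05.

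**3. The same formula with the odds ratios of 3.3.2**

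The plan gives no discordance rates for POC versus GenScript, so p01 is an assumption throughout. I read the odds ratios as ratios of discordant counts, as in 3.3.1.

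- *IgM, OR 7.5.* At p01 = 0.005, m = 15.9 and P = 0.882, giving power 0.955. At p01 = 0.0066 it is 0.99. An exact calculation of the uncorrected McNemar test is somewhat lower at the bottom of this range (0.91 at p01 = 0.005). A split of 30/4 in 302 (p01 = 0.013) fits both the odds ratio and p<0.001, and gives above 0.999 either way.
- *IgG, OR 1.1.* Power is 0.034, 0.042, 0.048, 0.062 and 0.067 for p01 = 0.01, 0.03, 0.05, 0.10 and 0.12. The formula counts rejection in one direction only, so it can fall below 0.05.

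The IgG split is not pinned down by p = 0.82. Under an uncorrected test 10/9 fits (19/302 = 6.3% discordant). Under a corrected or exact test 39/36 fits (75/302 = 24.8%). Exact rejection probabilities of the uncorrected McNemar test at N = 375 are 6.1% and 6.7%, so the conclusion does not depend on the split.

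**4. What 3.3.2 leaves out**

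Its data are central, by isotype, on stored plasma. Nothing covers the local fingerstick result, LumiraDx, or the IgM-or-IgG result that Section 2.3.2 prescribes when RightSign is treated simply as positive or negative.

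**5. Precision of percent agreement**

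Half-width = 1.96√[0.94 × 0.06/n], with 94% agreement assumed.

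- 46% seropositive (the TICO placebo figure in Section 2.2): about 172 GenScript-positive and 203 negative, so 3.5 and 3.3 points.
- 80% seropositive (assumption, since the field test may enrol vaccinated people): 300 positive and 75 negative, so 2.7 and 5.4 points.

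**The case against.** A reader might infer that the primary objective has no analysis and no power statement. The documents do not support that. Section 4.3 names McNemar's test and confidence intervals for exactly this comparison, and Section 3.3.2 discusses its power in words, carrying over the reasoning of 3.3.1. What is missing is the designation, the significance level, the missing-pair rule and a number.

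A reader might also infer that the true power is about 6% rather than 83%. That is a false contrast: 6% is power at odds ratio 1.1, where the assays barely differ, and 83% is power at 2.6. Low power there is expected, and Section 3.3.2 discloses it. The 1.1 also comes from central IgG on stored specimens, not from the local result.

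Nor is the 83% wrong in itself. Section 1 and the Table 5 caption speak of two assays in general. Only the heading of 3.3.1 and its remark about absent data tie the scenario to local versus central, and the figure would hold for local POC versus GenScript under the same inputs.

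Finally, primary in Section 4.2 could mean the main test of that section, as against its modelling and subgroup work. On that reading, however, no field-test analysis is designated primary at all, and the gap remains. It is also fair that the IgM-or-IgG rule does not exclude isotype-specific comparisons, and that both comparisons will be run on the same participants with the same test.

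**Conclusion.** The concern holds as a wrong designation. The primary label, the 0.05 level, the missing-pair rule and the only numeric power scenario are attached to secondary objective 3. The stated primary objective has an analysis but no designation, and a verbal power rating for central RightSign by isotype but no figure for the results it concerns.

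The 83% is sound arithmetic. It carries over to the primary objective only if odds ratio 2.6 and p01 = 0.03 are assumed there, and the plan's preliminary data support neither an IgM nor an IgG odds ratio near 2.6. The resulting power runs from about 0.03 to 0.07 up to above 0.95. Where the IgM-or-IgG composite, the local result or LumiraDx falls in or around that range cannot be told from the documents. All of these figures rest on assumed discordance, and the precision figures on assumed agreement and seropositivity.

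This should be corrected before analysis, because it decides which result is reported as primary.

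**What to change.** - In Section 4.3, designate local POC versus GenScript as the primary analysis for each platform, with the 0.05 level and the missing-pair rule. Label Section 4.2 as the analysis of secondary objective 3. If the sponsor did intend local versus central as primary, Sections 1 and 3.2.1 should be changed instead.
- In Sections 1 and 3.3.1, name the comparison to which the 83% refers.
- In Section 3.3.2, state numeric power or precision for the primary comparison with its assumed odds ratio and discordance. For RightSign, re-tabulate the IgM-or-IgG result from the 302 participants already in hand. For LumiraDx and the local result, show a range.
- Add positive and negative percent agreement with 95% confidence intervals alongside McNemar's test. That test asks whether two positive rates are equal, not whether the results are associated, so it does not by itself answer an objective worded as association. Show the precision under more than one seropositivity assumption.

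The cost is protocol wording and one re-tabulation of existing data, with no added participants. The downside is that the headline 83% no longer stands for the primary objective unless its inputs are justified there.

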3.3 Sample Size and Statistical Considerations

3.3.1 Local versus central POC test result

The power for comparisons of results from paired qualitative tests on specimens was assessed using Schlesselman's formula for the power of McNemar's chi-square test¹⁰. This requires specification of the odds ratio and the probability of 1 test being positive when the other is negative (denoted p_{01} in the table). Table 1 shows the power as it depends on these 2 parameters with a sample size of 375. By taking the odds ratio to be greater than 1 we are assuming that p_{01} is the smaller of the 2 probabilities of 1 test being positive while the other is negative. For example, $p_{01}=0.01$ and an odds ratio of 2.2 implies that the 2 probabilities that one test is positive while the other is negative are 0.01 and 0.022, and the probability that the 2 tests agree is 96.8%. As can be seen in Table 5, with a sample size of 375 the power of the test is low in this scenario (0.24), but this is fairly strong agreement across the assays. As can be seen from the same table, the test will have over 80% power if $p_{01}=0.03$ and the odds ratio is at least 2.6. This corresponds to the discordance probabilities of 0.03 and 0.078 and the corresponding probability that the 2 tests agree is 89.2%. With this configuration of probabilities for test agreement the standard error for the difference in the probability that the 2 tests are positive is 0.023. There is currently no data available for this comparison.

| Odds ratio | $p_{01}=0.01$ | $p_{01}=0.03$ | $p_{01}=0.05$ |
|------------|---------------|---------------|---------------|
| 2.0 | 0.19 | 0.49 | 0.72 |
| 2.1 | 0.21 | 0.56 | 0.79 |
| 2.2 | 0.24 | 0.62 | 0.85 |
| 2.3 | 0.27 | 0.68 | 0.89 |
| 2.4 | 0.30 | 0.74 | 0.93 |
| 2.5 | 0.33 | 0.79 | 0.95 |
| 2.6 | 0.36 | 0.83 | 0.97 |

Table 5: The power of McNemar's chi-square test for testing the agreement of 2 assays as it depends on the odds ratio and the smaller of the 2 probabilities for test discordance. This assumes the sample size is 375.

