4.3 Local and Central POC Test Result versus GenScript cPass Assay

The GenScript assay will also be conducted on the specimens at the central laboratory. The locally and centrally determined POC results will be compared to the GenScript result using McNemar's chi-square test and will be supplemented by 95% CIs for the difference in the probability of testing positive. Investigation of site effects and test performance in subgroups will be pursued as described in Section 4.2.

4.4 Association of POC Test Results with TICO Outcomes: A Nested Case-Control Study of Completed TICO Trials

TICO specimens selected for the case-control study will be shipped from the repository at Advanced Biomedical Labs LLC to the central laboratory for analysis. The Fine-Grey approach to competing risk regression will be used to test for an association between the POC test result and time to sustained recovery while controlling for the parent sub-study effect. A significance level of 0.05 will be used to test the null hypothesis that the regression coefficient associated with the presence of antibodies at baseline is zero. The association between baseline POC test results and time to death will be investigated using Cox models stratified by parent sub-study. The association between baseline POC test results and the primary safety composite at days 5, 28 and 90 will be investigated using logistic regression models that control for parent sub-study.

Finally, data will be pooled from the field test and the stored specimens for all qualitative assays conducted to test for differences. This would include the local POC, central POC, and GenScript results from the field test, the GenScript result for the stored specimens and the POC results for the stored specimens. This analysis will use generalized estimating equations for binary outcomes with effects for the type of assay (3 values), if the assay was conducted locally or centrally, and in which protocol/sub-study the participant enrolled. The association due to the specimen coming from the same person will be accounted for by including this information as a clustering effect in the model. Tests for differences in the assays will be based on the Wald test for the regression coefficients for the assays. No multiplicity adjustment will be made for these tests.

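### Section 4.3 would judge POC performance against GenScript across subgroups with a term that compares positivity, so a gap in antibody prevalence can mimic or hide a difference in agreement

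*Combined protocol and SAP*

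**What the plan says.** For local versus central runs of the same POC assay, Section 4.2 specifies "generalized estimating equations for Bernoulli outcomes using a logistic link", with the test result as outcome and fixed effects for test type and site. It adds that "the interaction between site and test type will be investigated". For age, immunocompromise and vaccination status it says "These subgroup analyses will test for an interaction between group membership and test type".

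Section 4.3 compares local and central POC results with GenScript and states: "Investigation of site effects and test performance in subgroups will be pursued as described in Section 4.2".

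The logistic link is written for the site model. Carrying it to the subgroup tests is the natural reading, though it is not repeated. Neither section includes a term for antibody status or for the reference result. Neither names positive or negative agreement, sensitivity, specificity or kappa by subgroup.

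**The concern.** In a marginal model for a positive result, the group-by-test-type term asks whether the POC-to-GenScript odds ratio of testing positive is the same in each group. That odds ratio depends on the POC test's agreement with GenScript and also on the share of the group that is GenScript-positive. The plan itself treats vaccination and similar characteristics as possible drivers of antibody results (Section 3.2.2, secondary objective 6, and the last paragraph of Section 4.2), so that share may well differ between groups.

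Two misreadings are possible. A significant term could be reported as the POC test working differently in vaccinated patients when only prevalence differs. A null term could be reported as uniform performance when the POC test misses more GenScript-positives in one group. The second matters because Section 2.1 treats false negatives as the main worry if neutralizing antibodies carry a safety concern in seropositive patients.

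**Working it through.** **Inputs from the documents.** "Sample size for the cross-sectional study is targeted at 375"; 46% GenScript-positive in the TICO placebo group (Section 2.2).

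**Assumptions.** The documents do not give POC agreement with GenScript by subgroup, subgroup sizes, subgroup positivity or a level for the interaction tests. I take a 187/188 split, two-sided 0.05, positive agreement (PPA) 92% and negative agreement (NPA) 97% in both groups, and 46% positive in one group. The share in the other group is varied.

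**The plan's own figure.** The plan gives power only for the overall McNemar test: "the study will have 83% power for detecting a difference in the probability of a positive test between 2 assays", at discordance 0.03 and 0.078. With P = 2.6/3.6 = 0.722 and 375 × 0.108 = 40.5 expected discordant pairs, Φ[(0.222 × √40.5 − 1.96 × 0.5)/√(0.722 × 0.278)] = Φ(0.97) = 0.83. It reproduces. The plan gives no operating characteristics for the interaction tests.

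**Step 1: positivity and odds ratio.** With π the GenScript-positive share, POC positivity is l = π·PPA + (1 − π)(1 − NPA), and the odds ratio is [l/(1 − l)]/[π/(1 − π)].

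- π = 0.46: l = 0.4232 + 0.0162 = 0.4394; odds ratio 0.920.
- π = 0.80: l = 0.736 + 0.006 = 0.742; odds ratio 0.719.

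Agreement is identical, yet the ratio of odds ratios is 0.719/0.920 = 0.781 (log −0.247).

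**Step 2: chance of rejection.** In a group of size n, the variance of the logit difference is (1/n)[1/v₁ + 1/v₂ − 2c/(v₁v₂)], with v₁ = l(1 − l), v₂ = π(1 − π) and c = π·PPA − lπ.

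- π = 0.80: (5.224 + 6.250 − 9.298)/187 = 0.0116.
- π = 0.46: (4.060 + 4.026 − 7.226)/188 = 0.0046.

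The standard error is √0.0162 = 0.127, so z = −1.94 and the test rejects in about 49%.

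| Share in other group | POC positivity | Odds ratio | Ratio to 46% group | Rejection, formula | Rejection, simulated |
|---|---|---|---|---|---|
| 46% | 0.439 | 0.920 | 1.00 | 5% | about 5% |
| 58% | 0.546 | 0.872 | 0.95 | 9% | about 8% |
| 70% | 0.653 | 0.806 | 0.88 | 23% | about 22% |
| 80% | 0.742 | 0.719 | 0.78 | 49% | about 48% |
| 90% | 0.831 | 0.546 | 0.59 | 80% | about 85% |

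Repeated simulations ranged over 45–50% at a share of 80% and 84–88% at 90%. Fisher tests within GenScript-positives and within GenScript-negatives each stayed below 5%.

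**Step 3: masking.** Let PPA be 80% in the 46% group and 92% in the 80% group, with NPA 97% in both. In the 46% group, l = 0.368 + 0.0162 = 0.3842 and the odds ratio is 0.732. In the other it is 0.719, as before. The ratio is 0.98, so a 12-point deficit nearly cancels. The planned test rejects in about 6%; a test among GenScript-positives rejects in about 71%.

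**Step 4: does the same hold in Section 4.2?** There both results come from one assay. If local and central runs share sensitivity and specificity, their positivity is equal at every prevalence, the interaction is exactly zero, and the planned test rejects in about 5%. Conditioning on the central result does worse. With sensitivity 92%, specificity 97% and independent errors in both runs, agreement among central-negatives is [π(0.08)² + (1 − π)(0.97)²]/[0.08π + 0.97(1 − π)]. This is 91%, 83%, 75% and 59% at π = 46%, 70%, 80% and 90%. A two-degree-of-freedom test conditional on the central result then rejects in about 30%, 64% and 95% at 70%, 80% and 90% versus 46%.

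Under the same errors, agreement among central-positives moves far less: 0.3898/0.4394 = 89% at 46% and 0.7619/0.831 = 92% at 90%.

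**The case against.** The strongest reply is that Section 4.2 describes its term simply as group by test type and does not call it accuracy. With no handling effect it gives no false signal there, and a conditional test would create one. That stands, and it confines the point to Section 4.3, where the same analysis is labelled as performance.

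It is also fair that a false signal needs both unequal positivity on the two assays and a wide gap in shares. At 58% versus 46% the excess over 5% is small. These are secondary analyses. The plan also examines test failures and timing by site (Section 4.1) and the quantitative LumiraDX result (Section 4.5), so the interaction is not its only evidence on where the tests can be relied on.

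A reader might infer that the planned tests will flag false differences throughout, including local versus central. The documents do not support this: they give no subgroup shares, and in Section 4.2 the effect vanishes when both runs make the same errors. At the Table 5 design point ("This corresponds to the discordance probabilities of 0.03 and 0.078"), with shares of 80% and 46%, the rate is only about 12–17% when the discordance falls entirely among antibody-positive or entirely among antibody-negative people. A reader might also blame the logit scale. That is only part of the cause: if the two tests differ in sensitivity alone, the risk difference also changes with prevalence.

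**Conclusion.** The point holds for Section 4.3. The planned interaction compares positivity and cannot carry a conclusion about agreement with GenScript by subgroup or site group. Under the stated assumptions the false-signal rate runs from about 8% at a modest gap in shares (58% versus 46%) to about 85% at a very wide one (90% versus 46%). A 12-point deficit in positive agreement can go almost unseen. These are illustrations, since subgroup shares, subgroup sizes and agreement are all assumed. The case is strongest for vaccination, if positivity there differs widely. The primary McNemar analysis and the planned interaction in Section 4.2 are not undermined. What is needed is a change of reporting and labelling.

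**What to change.** In Section 4.3 only:

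- Report positive and negative percent agreement of each POC result with GenScript, by subgroup and site group, with 95% CIs.
- Test the subgroup difference in the POC result among GenScript-positive participants. Show the same comparison among GenScript-negative participants as descriptive support.
- Label the group-by-test-type term as a comparison of positivity, not of performance.

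In Section 4.2, keep the planned interaction, described as a comparison of positivity. Do not replace it with tests conditional on the central result.

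The cost is SAP wording, using data already to be collected. Negative agreement will be imprecise where few participants are GenScript-negative. Because GenScript is itself imperfect, negative agreement shifts with antibody prevalence, so it must be read as agreement with GenScript and not as accuracy. With 15 participants per site, agreement should be shown for grouped sites, which Section 4.2 already allows.
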